3 OBJECTIVES AND ENDPOINTS

3.1 STUDY OBJECTIVES

PRIMARY OBJECTIVES

- To assess the rate of undetectable minimal residual disease (U-MRD) in subjects with CLL treated with the combination of ublituximab and umbralisib with either venetoclax, ibrutinib or acalabrutinib

SECONDARY OBJECTIVES

- To assess safety and tolerability of ublituximab and umbralisib with venetoclax, ibrutinib or acalabrutinib
- To determine the time to U-MRD at planned sequential response assessments
- To determine progression free survival and time to second objective disease progression, from time of initiation of ublituximab and umbralisib with venetoclax, ibrutinib or acalabrutinib
- To determine the durability of clinical benefit after treatment discontinuation as measured by duration of peripheral blood U-MRD response and treatment-free survival
- To determine the overall response rate, complete response rate, U-MRD rate, and PFS to re-treatment with ublituximab and umbralisib with venetoclax, ibrutinib or acalabrutinib in subjects who progress following achievement of U-MRD followed by treatment-free observation.

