5.4 RETREATMENT PHASE

Study Schema for Re-Treatment

*Progression Of Disease (PD) – Defined per the iwCLL Criteria (Hallek 2018)
U2 – ublituximab and umbralisib; IB – ibrutinib; ACALA – Acalabrutinib; VEN – venetoclax; MRD – minimal residual disease; EOS – end of study

Subject on treatment-free observation who subsequently develop clinical progression requiring treatment per iwCLL criteria (Hallek, et al., 2018) after 6 months of treatment-free observation will be retreated with the triple combination regimen that was previously received. Subjects who progress within 6 months of treatment-free observation discontinue from the study.

For subjects enrolled in Cohort A, retreatment will consist of 2 cycles of ibrutinib followed by treatment with ublituximab and umbralisib with ibrutinib cycles 3 through 26 of retreatment. The previously tolerated ibrutinib dose should be considered but is at investigator discretion (maximum dose 420mg daily).

For subjects enrolled in Cohort B, venetoclax should be initiated per the package insert. The target ramp-up dose should be considered based on the previously tolerated dose but is at investigator discretion (maximum dose 400mg daily). Retreatment will consist of 2 cycles of venetoclax followed by treatment with ublituximab and umbralisib with venetoclax cycles 3 through 26.

For subjects enrolled in Cohort C, retreatment will consist of 2 cycles of acalabrutinib followed by treatment with ublituximab and umbralisib and acalabrutinib cycles 3 through 26 of retreatment. The previously tolerated acalabrutinib dose should be considered but is at the investigator discretion.

Clinical response and U-MRD rate will be studied upon retreatment. If subjects achieve U-MRD status in the peripheral blood, MRD will be assessed by peripheral blood 4 weeks later to confirm U-MRD. Retreatment will continue until the occurrence of confirmed U-MRD response in the peripheral blood, completion of 26 cycles (24 cycles of triplet therapy), UTX-TGR-208

Version 2.0 Dated: 30 July 2020

definitive disease progression, unacceptable toxicity, or withdrawal from the study due to investigator decision or other reasons. Subjects who discontinue study treatment and have not progressed will continue to be followed for disease progression.

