7.2 STUDY ASSESSMENT AND TREATMENT SCHEDULE - TREATMENT FREE OBSERVATION

Cycle = 28 days	Treatment-Free Observation (TFO) Visits ¹	
Procedures/Days ²	TFO1 Cycle 1 Day 1	TFO Subsequent Day 1 Every 3 Cycles for 24 cycles and every 6 cycles thereafter
ECOG	X	X
Physical Examination	X	X
Vital Signs ³	X	X
Hematology	X	X
Chemistry	X	X
PB MRD ⁴		X
AE Evaluation	X	X
Con Meds	X	X

¹ At completion of 24 cycles with no progression of disease (POD), confirmed U-MRD, or discontinuation of treatment due to toxicity in absence of POD, subjects will enter a treatment-free observation period. Study assessments will be completed every 3 cycles for 24 cycles from discontinuation of any study drug.

² All TFO visits have a +/- 14 day window.

³ Vital signs to include temp, BP, HR, and respirations

⁴ Subjects on treatment-free observation with U-MRD should have peripheral blood MRD assessments approximately every 12 weeks +/- 2 weeks prior to Cycle 24 and every 24 weeks +/- 2 weeks, unless clinically indicated sooner, after Cycle 24. For subjects entering treatment-free observation with D-MRD, no PB MRD is required. For subjects entering TFO due to discontinuation of treatment due to toxicity in absence of POD, MRD should be done at TFO1. If U-MRD repeat MRD in PB in 4 weeks, if D-MRD, no further PB MRD is required.

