11.6.1.2.7 DURATION OF PERIPHERAL BLOOD UNDETECTABLE MINIMAL RESIDUAL DISEASE RESPONSE

Duration of U-MRD response is defined as the interval from the first documentation of undetectable MRD to the earlier of the first documentation of presence of MRD or death from any cause. The Kaplan-Meier estimate for the duration will be based on subjects who achieve U-MRD response. For subjects alive without presence of MRD, it will be censored at the last MRD assessment.

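### Duration of U-MRD can censor a subject who progresses early off treatment at a negative test taken before the progression

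*Combined protocol and SAP*

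**What the plan says.** - **Event.** In Section 11.6.1.2.7 the definition reads: "interval from the first documentation of undetectable MRD to the earlier of the first documentation of presence of MRD or death from any cause". Section 3.2 and the synopsis use the same definition.
- **Analysis set.** "The Kaplan-Meier estimate for the duration will be based on subjects who achieve U-MRD response".
- **Censoring.** "For subjects alive without presence of MRD, it will be censored at the last MRD assessment". There is no exception for progression or new therapy, and no sensitivity analysis is described.
- **Purpose.** Section 3.1 sets the objective as "durability of clinical benefit after treatment discontinuation as measured by duration of peripheral blood U-MRD response and treatment-free survival".
- **MRD testing off treatment.** Section 7.2, footnote 4: "Subjects on treatment-free observation with U-MRD should have peripheral blood MRD assessments approximately every 12 weeks +/- 2 weeks prior to Cycle 24". After Cycle 24 the interval is 24 weeks. An extra test is foreseen only through the clause "unless clinically indicated sooner". The table has no blood MRD mark at the first visit of treatment-free observation (TFO); the footnote asks for one there only when treatment stopped for toxicity.
- **Early progression.** Section 5.4: "Subjects who progress within 6 months of treatment-free observation discontinue from the study". Section 5.6 agrees, and the synopsis calls these subjects refractory.
- **End of study (EOS).** In the Section 7.1 table the blood MRD row is blank at EOS. The Section 7.2 table has no EOS column.
- **Retreatment.** Section 7.3, footnote 11, asks for blood MRD within 30 days of restarting therapy.

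**The concern.** Loss of U-MRD can be recorded only if somebody takes a blood sample. A subject who progresses early in TFO is taken off study because of that progression, and nothing obliges the site to take an MRD sample first. The follow-up time then ends at the last negative test, and it ends because the subject has failed. Kaplan-Meier treats such a subject as having the same outlook as those still in remission, which is the opposite of what has been observed.

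The definition of progression does not prevent this. None of the events listed in Section 10.7 refers to blood MRD. They rest on nodes, spleen, liver, extranodal or other non-target disease, transformation, or cytopenia with marrow confirmation. A nodal progression with clear blood is therefore not an event for this endpoint, unless MRD later appears or the subject dies.

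At stake is the study's claim about how long benefit lasts once treatment stops on the strength of U-MRD. The subjects whom the protocol itself calls refractory can be counted as censored rather than as failures.

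**Working it through.** The plan has no figure to reproduce. Section 11.1 gives no power, target rate or assumed duration, and neither does Section 11.6.1.2.7. The check has two parts: tracing what happens to each kind of progressor, and a small illustration on assumed inputs.

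**1. Tracing the text**

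| Confirmed U-MRD subject in TFO | MRD test near progression | Result as written |
|---|---|---|
| Progresses within 6 months | Only if it falls at a scheduled MRD visit or the site orders one; none at EOS | Without a positive test, censored at the last negative test. Before the first TFO sample, this can be the 4-week confirmation test |
| Progresses later and is retreated | Within 30 days of restarting | Event if that test is positive |
| Nodal progression, blood MRD negative | Any test is negative | Not an event |

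The neighbouring endpoints do not fully close the gap. Treatment-free survival (Section 11.6.1.2.8) ends at retreatment or death and otherwise censors at the last date known alive. An early progressor is not retreated on study, so it is unclear whether that subject ever becomes an event. PFS (Section 11.6.1.2.4) does count the progression, but it runs from enrollment, not from U-MRD or from stopping treatment.

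**2. Illustration**

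Assumed inputs, none from the documents except where stated:
- n responders. The synopsis gives up to about 28 subjects per cohort, but no responder number.
- Weeks counted from first U-MRD: confirmation at week 4 (synopsis), TFO from about week 8, TFO MRD tests at weeks 20, 32, 44 and 56.
- k subjects progress at week 18 or week 30 with no positive MRD test.
- Of the other n - k, m (20%, rounded) are MRD-positive at week 44. The rest are followed past week 52.

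Week-52 Kaplan-Meier estimates:
- As written, the k subjects are censored before week 44: S = (n - k - m)/(n - k).
- With progression as an event: S = [(n - k)/n] × [(n - k - m)/(n - k)] = (n - k - m)/n.
- Difference = (k/n) × the as-written estimate.

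| n | k | m | As written | Progression as event | Difference |
|---|---|---|---|---|---|
| 14 | 0 | 3 | 11/14 = 0.786 | 11/14 = 0.786 | 0 |
| 14 | 1 | 3 | 10/13 = 0.769 | 10/14 = 0.714 | 0.055 |
| 14 | 2 | 2 | 10/12 = 0.833 | 10/14 = 0.714 | 0.119 |
| 14 | 3 | 2 | 9/11 = 0.818 | 9/14 = 0.643 | 0.175 |
| 7 | 1 | 1 | 5/6 = 0.833 | 5/7 = 0.714 | 0.119 |
| 21 | 1 | 4 | 16/20 = 0.800 | 16/21 = 0.762 | 0.038 |

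Both progression times give the same values, because no other event occurs before week 44. Compare within a row: m changes between rows through rounding.

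A simulation with 14 responders and 1,500 runs per setting gave the same direction. With a true 12-month MRD-relapse-free probability of 0.80, the week-56 estimates (as written against progression as event) were:
- 5% progressing early: 0.786 against 0.746
- 10%: 0.787 against 0.706
- 20%: 0.783 against 0.626

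Over true 12-month values of 0.6 to 0.9 and early-progression shares of 5% to 20%, the gap was about 3 to 18 percentage points. At a share of zero there was none.

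**The case against.** The strongest reply is that the exposed group is narrow and the endpoint is defensible as named.

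- Extra MRD tests are allowed when clinically indicated, and a suspected progression is an obvious occasion. This stands in part: the clause permits a test but does not require one.
- In Section 7.2, examination, hematology and blood MRD fall at the same visits after the first, and the table schedules no imaging. Much progression would therefore be found on a day when MRD is drawn. This stands for progression found at those visits, but not for an unscheduled presentation or for clear blood.
- A reader might infer that every progressor escapes the endpoint. The documents do not support that. Retreated subjects have MRD tested within 30 days of restarting, and Section 5.6 does not take a subject off study merely for progressing in TFO after 6 months.
- Time to MRD recurrence is a legitimate quantity, Section 3.1 pairs it with treatment-free survival, and PFS reports the progressions. This is a fair reason to keep the MRD-only analysis. It does not make that analysis, alone, a measure of clinical benefit.
- The endpoint is secondary and descriptive, in uncontrolled cohorts, with no hypothesis test. This stands, and it sets the severity.

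**Conclusion.** The gap is real but limited. It concerns mainly U-MRD subjects who progress within 6 months of TFO without a positive MRD test, plus any progression with negative blood MRD. For durability of clinical benefit, their censoring is informative. From the progression date onward the bias is upward if such a subject occurs. It is nil if every progressor is MRD-positive by then.

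The size cannot be derived from the documents. With few responders per cohort, one or two such subjects can move the estimate by several percentage points: 5.5 points for one and 11.9 for two, under the assumed 14 responders.

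Three stronger readings are tempting and should not be drawn:
- That early failures are dropped from the analysis. They are censored, and they stay in the risk set until their last MRD test.
- That durability will be overstated. This depends on whether such subjects occur.
- That the median is inflated by 1/(1 - s), where s is the share of failures without a positive MRD test. This needs s to be constant for all time, whereas the exposure is concentrated in early TFO. If s acts only over the first T months and hazards are exponential with an assumed 18-month median, the as-written median is 18 + sT. With an assumed T of 8 months, this is 18.8, 19.6 and 20.4 months for s of 10%, 20% and 30%.

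Severity is low, and the change is a cheap improvement.

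**What to change.** In Section 11.6.1.2.7, and to match in Section 3.2 and the synopsis, end the duration at the earliest of documented MRD, definitive disease progression, start of retreatment or other recorded anti-CLL therapy, or death. Continue to censor subjects with none of these at the last MRD assessment. Report the MRD-only version beside it as a sensitivity analysis, with the number of subjects who progressed without a positive MRD test.

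The cost is analysis wording. Progression and on-study retreatment dates are already needed for PFS and treatment-free survival. The reported duration may be slightly shorter, and therapy given after a subject leaves the study may be incompletely captured, so progression will carry most of the added events.

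An MRD sample at progression or EOS would narrow the gap too. It would change the assessment schedule, however, and would not capture a progression with negative blood, so it is no substitute for the change of definition.

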11.6.1.2.8 TREATMENT-FREE SURVIVAL

Treatment free survival (TFS) is defined as the interval from drug discontinuation to the earlier of initiation of retreatment for disease progression requiring treatment or death from any cause. Disease progression requiring treatment is based on standard criteria (Hallek, et al., 2018). TFS will be estimated using the Kaplan-Meier method for subjects who discontinued initial study treatment. For subjects alive without initiation of retreatment, it will be censored at the last date known alive.

11.1 SAFETY ANALYSES

Safety evaluations will be based on the incidence, intensity, and type of adverse events, as well as on clinically significant changes in the subject's physical examination, vital signs, and clinical laboratory results. Safety analyses will be performed using the safety population. Safety variables will be tabulated and presented by the treatment regimens received. Exposure to study treatment and reasons for discontinuation of study treatment will also be tabulated.

12 ADVERSE EVENT REPORTING AND CRITERIA

12.1 ADVERSE EVENT

An adverse event (AE) is any untoward medical occurrence in a subject or clinical investigation subject administered a pharmaceutical product. An AE does not necessarily have to have a causal relationship with this treatment. An AE can therefore be any unfavorable and unintended sign (including an abnormal laboratory finding, for example), symptom, or disease temporarily associated with the use of a medicinal product, whether or not considered related to the medicinal product. This includes any occurrence that is new in onset or aggravated in severity or frequency from the baseline condition. An AE can occur at any time, including during screening, run-in or washout periods, even if no study drug has been administered. It is the responsibility of the Investigator, based on his/her knowledge and experience, to determine which untoward medical occurrences should be considered AEs.

12.2 CRITERIA FOR SERIOUS ADVERSE EVENT

The criteria for serious adverse events (SAEs) are described below. The Investigator is responsible for ensuring that all staff involved in the study are familiar with the content of this section.

An SAE is defined as any untoward medical occurrence that meets at least one of the following criteria:

- **Results in death;**

In the case of deaths, the event(s) leading to the death should be recorded and reported as SAE(s) with the outcome "Fatal". The death itself will not be reported as an SAE, unless the cause of the death is unknown (e.g. in case of unexplained or sudden death).

- **Is life-threatening;**

The term "life-threatening" refers to an event in which the subject is at immediate risk of death at the time of the event; it does not refer to an event which hypothetically might cause death if it was more severe.

- **Requires inpatient hospitalization or prolongation of existing hospitalization;**

- **Results in persistent or significant disability/incapacity;**

A disability is defined as any substantial disruption of a subject's ability to conduct normal life functions.

- **Is a congenital anomaly/birth defect; and/or**
- **Is medically important.**

Medical and scientific judgment must be exercised in deciding whether an AE is considered "medically important". Medically important events may not be immediately life-threatening or result in death or hospitalization but may jeopardize the subject or may require intervention to prevent one of the other outcomes listed in this definition. Examples of such events are intensive treatment in an UTX-TGR-208

Version 2.0 Dated: 30 July 2020

emergency room or at home for allergic bronchospasm; blood dyscrasias or convulsions that do not result in hospitalization; or development of drug dependency or drug abuse.

Progression of disease (including fatal outcomes), if documented by use of appropriate method (for example, as per IWCLL Hallek et al., 2018) should not be reported as an SAE.

Situations Not Considered SAEs:

Treatment within or admission to the following facilities is not considered to meet the criteria of “in-patient hospitalization” (although if any other SAE criteria are met, the event must still be treated as an SAE and immediately reported (i.e. could meet the definition of important medical event)):

- Emergency Department or Emergency Room
- Hospitalization for drug administration, diagnostic procedure, or social circumstances
- Outpatient or same-day surgery units
- Observation or short-stay unit
- Rehabilitation facility
- Hospice or skilled nursing facility
- Nursing homes, Custodial care or Respite care facility

Hospitalization during the study for a pre-planned surgical or medical procedure (one which was planned prior to entry in the study), does not require reporting as an SAE to the Sponsor, but if hospitalization is prolonged due to an event this would be reportable to Sponsor or designee.

Serious Versus Severe AEs:

It is important to distinguish between “serious” and “severe” AEs, as the terms are not synonymous. Severity is a measure of intensity; however, an AE of severe intensity need not necessarily be considered serious. For example, nausea which persists for several hours may be considered severe nausea but may not be considered an SAE. On the other hand, a stroke which results in only a limited degree of disability may be considered only a mild stroke but would be considered an SAE. Severity and seriousness should be independently assessed when recording AEs and SAEs on the eCRF.

12.3 ADVERSE EVENTS / SERIOUS ADVERSE EVENT GRADING

The Investigator should use the NCI Common Terminology Criteria for Adverse Events (CTCAE) Version 5.0 for grading severity of AEs. A copy of the CTCAE version 5.0 can be downloaded from the [CTEP web site](https://ctep.cancer.gov/protocolDevelopment/electronic_applications/docs/CTCAE_v5_Quick_Reference_5x7.pdf#search=%22ctcae%205.0%22) https://ctep.cancer.gov/protocolDevelopment/electronic_applications/docs/CTCAE_v5_Quick_Reference_5x7.pdf#search=%22ctcae%205.0%22

For AEs not covered by the NCI-CTCAE grading system, the following definitions should be used:

- **Grade 1** Mild; asymptomatic or mild symptoms; clinical or diagnostic observations only; intervention not indicated.
- **Grade 2** Moderate; minimal, local or noninvasive intervention indicated; limiting age-appropriate instrumental ADL*.
- **Grade 3** Severe or medically significant but not immediately life-threatening; hospitalization or prolongation of hospitalization indicated; disabling; limiting self-care ADL**.
- **Grade 4** Life-threatening consequences; urgent intervention indicated.

- **Grade 5** Death related to AE.

Activities of Daily Living (ADL)

*Instrumental ADL refer to preparing meals, shopping for groceries or clothes, using the telephone, managing money, etc.

- **Self-care ADL refer to bathing, dressing and undressing, feeding self, using the toilet, taking medications, and not bedridden.

12.4 ADVERSE EVENTS (AE'S) AND TREATMENT EMERGENT ADVERSE EVENTS (TEAE'S)

All AEs and SAEs occurring on study will be listed by subject. The frequency and percentages of subjects with treatment-emergent adverse events (TEAEs) will be tabulated by system organ class (SOC) and preferred term (PT), where treatment-emergent is defined as any AE that:

- Occurs after first dosing of study medication and through the end of the study or up through 30 days after the last dose of study treatment, or
- Is considered treatment-related regardless of the start date of the event, or
- Is present before first dosing of study medication but worsens in intensity or the investigator subsequently considers treatment-related.

TEAEs that are considered at least possibly related to study treatment will be tabulated as well as deaths, SAEs, and events resulting in treatment discontinuation.

At each level of summarization, a subject will be counted only once for each AE, SOC, or PT experienced within that level. In the summation for AE severity, within each level of AE, SOC, or PT experienced, the one with the highest severity will be included. In the summation for AE's relationship to the study drug, within each level of AE, SOC, or PT experienced, the one with the closest relationship to the study drug will be included.

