4.1 INCLUSION CRITERIA

1. Subjects with CLL who are currently receiving treatment with ibrutinib, acalabrutinib or venetoclax for greater than or equal to 6 months.
2. Minimal residual disease (MRD) positive (D-MRD) as determined by central lab performed during screening period.
 - a. For subjects receiving venetoclax: response assessment demonstrating stable disease, partial response, or complete response AND detectable MRD in the peripheral blood (central lab).
 - b. For subjects receiving ibrutinib or acalabrutinib: response assessment demonstrating stable disease, partial response or partial response with lymphocytosis, or complete response AND detectable MRD in the peripheral blood (central lab).
3. Adequate organ system function, defined as follows:
 - a. Absolute neutrophil count (ANC) $\geq 1,000/\text{mm}^3$ (μL) / platelet count $\geq 50,000/\text{mm}^3$ (μL). Growth factor to maintain these counts is permitted during screening period and throughout the conduct of the trial.
 - b. Total bilirubin ≤ 1.5 times the upper limit of normal (ULN), unless a diagnosis of Gilbert's syndrome or an autoimmune hemolytic anemia.
 - c. Alanine aminotransferase (ALT) and aspartate aminotransferase (AST) $\leq 2.5 \times \text{ULN}$ if no liver involvement or $\leq 5 \times \text{the ULN}$ if known liver involvement.
 - d. Calculated creatinine clearance $>30 \text{ mL/min}$ (as calculated by the modified Cockcroft-Gault formula, MDRD formula, or 24-hour urine CrCl).
4. ECOG performance status ≤ 2 .
5. Male or female ≥ 18 years of age.
6. Ability to swallow and retain oral medication.
7. Female subjects who are not of child-bearing potential (see Appendix B- Contraceptive Guidelines and Pregnancy), and female subjects of child-bearing potential who have a negative serum pregnancy test within 3 days prior to Cycle 1, Day 1. Female subjects of child-bearing potential, and male partners must consent to use a medically acceptable method of contraception throughout the study period and for 4 months after the last dose of ublituximab or umbralisib, and for at least 30 days after the last dose of ibrutinib, acalabrutinib or venetoclax.
8. Willingness and ability to comply with trial and follow-up procedures and give written informed consent.

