12.5.1 RECORDING OF ADVERSE EVENTS

All adverse events of any subject during the course of the study will be reported on the case report form, and the investigator will give his or her opinion as to the relationship of the adverse event to study drug treatment (i.e., whether the event is related or unrelated to study drug administration – either ublituximab, umbralisib, venetoclax, ibrutinib). If the adverse event is serious, it should be reported as soon as possible and no greater than 24 hours to the sponsor or designee. Other untoward events occurring in the framework of a clinical study are also to be recorded as AEs (i.e., AEs that occur prior to assignment of study treatment that are related to a protocol-mandated intervention, including invasive procedures such as biopsies, medication washout, or no treatment run-in).

All AEs regardless of seriousness or relationship to ublituximab, umbralisib, venetoclax or ibrutinib from Cycle 1/Day 1 until 30 calendar days after discontinuation or completion of either protocol-specific treatment as defined by the protocol for that subject, are to be recorded on the eCRF.

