12.5.3 HANDLING OF ADVERSE EVENTS

All adverse events resulting in discontinuation from the study should be followed until resolution or stabilization. Subjects should be followed for AEs for 30 calendar days after discontinuation or completion of protocol-specific treatment (ublituximab, umbralisib, venetoclax, ibrutinib or acalabrutinib). All new AEs occurring during this period must be reported and followed until resolution unless, in the opinion of the investigator, these values are not likely to improve because of the underlying disease. In this case, the investigators must record his or her reasoning for this decision in the subject's medical record and as a comment on the eCRF. After 30 days, only AEs, SAEs, or deaths assessed by the investigator as treatment related are to be reported.

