12.6.2 SERIOUS ADVERSE EVENT REPORTING BY INVESTIGATORS

It is important to distinguish between “serious” and “severe” adverse events, as the terms are not synonymous. Severity is a measure of intensity; however, an AE of severe intensity need not necessarily be considered serious. For example, nausea which persists for several hours may be considered severe nausea but may not be considered an SAE. On the other hand, a stroke which results in only a limited degree of disability may be considered only a mild stroke but would be considered an SAE. Severity and seriousness should be independently assessed when recording AEs and SAEs on the eCRF.

Adverse events classified by the treating investigator as **serious** require expeditious handling and reporting to the Sponsor in order to comply with regulatory requirements. Serious adverse events may occur at any time from the signing of the informed consent form through the 30-day follow-up period after the last study treatment. Sponsor or designee should be notified of all SAEs, regardless of causality, within 24 hours of the first knowledge of the event by the treating physician or research personnel.

To report an SAE, see the appropriate form.

All SAEs (regardless of causality assessment) occurring on study or within 30 days of last study treatment should be immediately reported to the sponsor as SAEs within the CRF and on the SAE form followed until resolution (with autopsy report if applicable).

CLL progression or death due to CLL progression should be reported by the investigator as a serious adverse event only if it is assessed that the study drugs caused or contributed to the CLL progression (i.e. by a means other than lack of effect). Unrelated events of CLL progression should be captured on the appropriate eCRF.

The investigator must review and sign off on the SAE data on the SAE report. The SAE should be reported to the Sponsor at [contact] within 24 hours of the first knowledge of the event by the treating physician or research personnel on the SAE Form and followed until resolution (with autopsy report if applicable). When an SAE is reported to the sponsor or designee, the same information should be entered on the eCRF within 24 hours (1 business day). Transmission of the SAE report should be confirmed by the site personnel submitting the report.

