12.9.5 PRE-EXISTING MEDICAL CONDITIONS

A pre-existing relevant medical condition is one that is present at the start of the study. Such conditions should be recorded on the study's appropriate medical history eCRF. A pre-existing medical condition should be recorded as an AE or SAE only if the frequency, severity, or character of the condition worsens during the study. When recording such events on the appropriate SAE Report Form and/or AE eCRF, it is important to convey the concept that the pre-existing condition has changed by including applicable descriptors.

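### The treatment-emergent rule sets no onset limit for related events, so a screening-period event attributed to the background drug can be counted as emergent on the triplet

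*Combined protocol and SAP*

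**What the plan says.** Section 12.4 gives three alternative grounds on which an adverse event (AE) is treatment-emergent:

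1. Timing: "Occurs after first dosing of study medication and through the end of the study or up through 30 days after the last dose".
2. Relatedness: "Is considered treatment-related regardless of the start date of the event".
3. Pre-dose events: "Is present before first dosing of study medication but worsens in intensity or the investigator subsequently considers treatment-related".

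The same section counts a subject once per term and keeps the record with the highest severity and the closest relationship to study drug. The Safety Analyses text in Section 11 tabulates by regimen received, which means by triplet.

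**Status of the background drug.** Inclusion criterion 1 (4.1) takes subjects "currently receiving treatment with ibrutinib, acalabrutinib or venetoclax for greater than or equal to 6 months". The Study Drugs row of the synopsis lists all three background agents beside ublituximab and umbralisib. Section 12.5.1 asks for causality to "either ublituximab, umbralisib, venetoclax, ibrutinib", leaving out acalabrutinib. Section 12.5.3 names all three as protocol treatment. Section 12.5 is worded as if there were only two study drugs.

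**What gets recorded.** Section 12.5.1 starts general AE recording at Cycle 1 Day 1 and adds earlier events only if they are related to a protocol-mandated intervention. Section 12.9.5 makes a pre-existing condition an AE "only if the frequency, severity, or character of the condition worsens during the study". Against that, 12.1 says AEs can occur in screening, the schedule in 7.1 marks AE evaluation at screening, and 12.6.2 says "Serious adverse events may occur at any time from the signing of the informed consent form". After 30 days off treatment, 12.5.3 collects related events only.

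**The concern.** Where no study drug is taken before Day 1, an event that starts before Day 1 can hardly be judged drug-related, so a relatedness ground without an onset limit does little harm. Here one of the three drugs has been taken for months. A screening event can quite properly be attributed to it before any ublituximab or umbralisib has been given.

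Safety and tolerability of the combination is a secondary objective (3.1), and there is no control arm. Onset relative to the first ublituximab or umbralisib dose is therefore one of the few ways to separate what arose on the triplet from what was already there. Common terms overlap. Section 9.3 lists neutropenia, diarrhea and nausea as very common with ublituximab plus umbralisib. Section 9.5.1 gives 38.7%, 40.2% and 37.8% for the same terms with venetoclax. Those figures show only that the terms coincide; they are not rates for the screening period.

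**Working it through.** The documents give no figure on this point to reproduce. The check is a reading of the rules in sequence, followed by a simple illustration of size.

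**Step 1: does the event become a recorded AE?**

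- Toxicity present and stable when the study starts: medical history under 12.9.5. It does not reach 12.4.
- Toxicity that worsens after Cycle 1 Day 1: an AE, and treatment-emergent under any usual definition. No error.
- An event with onset between consent and Cycle 1 Day 1 (screening opens at day -28 in 7.1): a serious event is reportable under 12.6.2. A non-serious one may be recorded under 12.1 and 7.1, although 12.5.1 points the other way. Section 12.9.5 does not settle it, because it does not say whether the start of the study is consent or Cycle 1 Day 1.

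**Step 2: does 12.4 then count it?** Take a screening-onset event attributed to the background drug that does not worsen.

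- Ground 2 admits it, because the start date is irrelevant.
- Ground 3 also admits it if relatedness is judged later, because worsening is only one of two alternatives.
- Ground 1 should exclude it, but first dosing of study medication is not defined. If the background drug counts as study medication, that date lies at least 6 months before entry, and even unrelated screening events would pass.

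**Step 3: effect of the counting rule.** A hypothetical subject has Grade 3 diarrhea in screening, attributed to the background drug and resolved, then unrelated Grade 1 diarrhea after Cycle 1 Day 1. Under 12.4 the table shows one subject with related Grade 3 diarrhea. With an onset limit it shows unrelated Grade 1. Incidence is the same, but grade and relatedness are not.

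**Step 4: size.** The synopsis gives up to approximately 28 subjects per cohort. A subject whose only event for a term is such a pre-dose event adds 1/28 = 3.6 percentage points. If nobody truly had the term after dosing, one affected subject changes 0/28 (0%, exact 95% interval 0 to 12.3) into 1/28 (3.6%, 0.1 to 18.3). In a smaller cohort of n the weight is 1/n.

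The share of subjects affected, q, is not in the documents. For assumed values, the expected number is 28q and the chance of at least one is 1 - (1 - q)^28:

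| Assumed q | Expected number in 28 | Chance of at least one |
|---|---|---|
| 2% | 0.6 | 43% |
| 5% | 1.4 | 76% |
| 10% | 2.8 | 95% |
| 20% | 5.6 | 99.8% |

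**The case against.** The strongest reply is that 12.4 classifies only what has been recorded, and the recording rules keep most background toxicity out. Section 12.9.5 sends stable conditions to medical history, and 12.5.1 starts general recording at Cycle 1 Day 1. This stands. A reader might infer that months of accumulated ibrutinib, acalabrutinib or venetoclax toxicity will be reported as emergent; the documents do not support that. What remains is mainly the period from consent to Cycle 1 Day 1, plus any entries made against 12.9.5.

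Second, the relatedness ground has a proper use. Ground 1 can be read as ending 30 days after the last dose, while 12.5.3 still collects related events after that. A ground without a date limit keeps those late events in the tables, which matters with a long treatment-free period. This also stands, and it rules out simply deleting the ground.

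Third, the objective concerns the whole regimen, so background-drug toxicity arising on the triplet is in scope. That is right; only pre-dose onset is at issue. Nor do the documents support a complaint that cohorts become non-comparable: no between-cohort safety comparison is planned, and prior drug decides cohort membership.

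Fourth, the error overstates harm, touches no decision rule, and can be traced in the by-subject listing. True, but the summary tables would still be wrong for the affected terms.

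**Conclusion.** The point holds in a limited form. As written, 12.4 can count a non-worsening event from before Cycle 1 Day 1, attributed to the background drug, as a related treatment-emergent event of the triplet, and can let it set the subject's grade or relatedness for that term. This rests on two readings: that the background drugs are study drugs for causality, as most but not all sections say, and that some events between consent and Cycle 1 Day 1 are recorded, as 12.6.2 requires for serious ones.

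The size is up to 3.6 points per affected subject and term in a cohort of 28. A large shift in one term would need several subjects with the same preferred term, each with no later on-treatment event of that term. The number of such subjects is unknown and probably small. The primary endpoint is unaffected.

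**What to change.** Reword 12.4 so that:

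- A treatment-emergent AE is one with onset, or an increase in CTCAE grade over its pre-dose grade, on or after the first Cycle 1 Day 1 dose of ublituximab or umbralisib and through 30 days after the last dose of study treatment. For the re-treatment phase, the starting point is the first re-treatment dose.
- The relatedness ground is kept only for events with onset after that first dose, so that late related events collected under 12.5.3 stay in.
- The clause admitting a pre-dose event merely because it is later judged related is deleted.
- Pre-dose events are listed separately.

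The end date is needed. Without it, every unrelated event in treatment-free observation, where 7.2 continues AE evaluation, would count as emergent.

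Also reconcile 12.1, 12.4, 12.5, 12.5.1, 12.5.3, 12.6.2 and 12.9.5 on which drugs are study drugs (adding acalabrutinib to 12.5.1) and on when recording starts.

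The cost is a minor change to wording and programming. Pre-dose events remain in the by-subject listing, so no data are lost. One practical detail: 12.9.1 asks for a separate record only when a persistent event moves between Grades 1 or 2 and Grades 3 or 4. The eCRF guidance should therefore also capture smaller grade increases, which the existing worsening clause already needs.
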